Caregivers (Intervention): The intervention will be delivered in six individual hour-long sessions during three months by a trained and certified masters-level, mental health professional Program Coach, using the VAMC Memphis Caregiver Center’s national certifying procedures. These include didactic, knowledge test, and supervised role play of intervention components. The first consent and assessment visit will also be in the facility during a patient clinic visit; consent can be obtained by the Research Associate or Program Coach. At this visit, the Program Coach will also begin the Intervention process to establish rapport; subsequent caregiver REACH sessions, approximately every two weeks, will be in the facility, by telephone, or by telehealth, dependent on patient appointments and caregiver desire. All sessions will be taped and treatment fidelity will assess intervention delivery, receipt, and enactment.

STUDY FLOW CHART

First Visit Sequence

Data Collection. A trained masters-level Research Associate will collect data from Caregiver and Veteran by telephone or at clinic visits (which typically occur every three months) at baseline (first assessment and consent visit), end of intervention (3 months), and 6 months.

REACH VA MS STATEMENT OF WORK (SOW)

Task 1: Develop Manual of Operations (MOP)

Month 1

Activities

- Finalize REACH VA MS sessions format
- Finalize REACH VA MS materials
- Finalize screening materials
- Finalize data collection protocol/battery
- Develop and print brochures and posters

Products

- Program Coach notebook, topics and scripts
- Caregiver Notebook
- Screening forms and scripts
- Data collection forms, scripts and documentation
- Brochures and posters

Task 2: IRB approval

Month 1

Activities

- Develop all IRB documents

Products

- IRB study approval

Task 3: Train personnel

Month 1

Activities

- Train Program Coach and research associate

Products

- Trained and certified staff

Task 4: Recruitment and Randomization

Months 1-15

Activities

- Mail brochures

- Telephone and screen potential participants

Products

- Approximately 46 Caregivers/Veterans screened
- 25 pairs recruited

Task 5: Intervention

Months 1-20

Activities

- Schedule and provide intervention for Caregivers

Products

- Intervention sessions provided

Task 6: Data Collection/Data Entry/Cleaning

Months 1-24

Activities

- Collect Caregiver data at baseline, 3 and 6 months
- Collect Veteran data at baseline, 3, and 6 months

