Hypothesis 1: Veterans of Caregivers who receive the intervention will have significant improvement in outcomes including the Expanded Disability Status Scale (EDSS), timed up and go test (TUGT), self-efficacy, and depression.

Hypothesis 2: Caregiver participants will have significant improvement in outcomes including depression, burden, anxiety, and number of Veteran MS problems and safety alerts reported.

Flowchart of REACH VA MS Intervention Protocol

INTERVENTION - OVERVIEW

The REACH VA Program for the MS Pilot Project is delivered in six sessions over a three month period. The Program Coach can conduct sessions with the Caregiver either face to face (home or facility) or by telephone or telehealth format.

The first component of the REACH VA Program is to assess risk in the caregiving situation, and then address risks by engaging the Caregiver in problem solving and skills building techniques. The program emphasizes safety, health, social support, Caregiver physical and emotional well-being, stress management, and problem solving.

- Caregivers are usually a family member or someone with a significant personal relationship who provides substantial, necessary, regular or long-term care for a Veteran with MS and is receiving services at the VA.
- The REACH VA Program can be delivered face to face (in the home or facility) or by telephone or telehealth. The Program Coach will provide Six Individual Sessions.
- Practical elements or tasks to be completed during the sessions include:
 - **Risk Assessment**
 - o Assess Caregiver risk in Session 1 using Risk Assessment.
 - o Program Coach uses this assessment throughout the REACH VA Program to target certain Care Recipient problems or safety issues and/or Caregiver centered problems related to health, physical and emotional well-being, and social support.
 - **Education Tasks**
 - o Provide general information about care recipient's condition (MS).
 - o Present safety materials.
 - o Present health care issues and explain the Health Guide.
 - o Present chapters in the Caregiver Notebook on Mobility and Wellness for the Veteran.
 - o Present Exercise brochures (Exercise as Part of Daily Life and Minimizing Your Risk of Falls) and review the Physical Therapy Exercise Plan.
 - **Problem Solving Tasks around Caregiver Concern**
 - o Problem solve to identify Target Problem.
 - o Introduce Problem Solving Plan.
 - o After initial plan, review and modify Problem Solving Plan.
 - o Introduce Mobility Plan

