- ❑ This education and training is handled through two overarching approaches: reducing negative affect/mood and increasing positive affect/mood. The Program Coach helps the Caregiver reduce negative affect/mood (frustration/anger and sadness/depression) by learning to relax in the stressful situation, learning to appraise the Care Recipient's behavior more realistically, and learning to identify and challenge negative thinking. The Program Coach works with the Caregiver to increase positive mood through an awareness of the connection between mood and activities, along with strategies for increasing simple everyday pleasant activities.

Session Structure.

- 1) Each individual session will occur bi-monthly for 6 times over three months. Each session will last about an hour. Sessions can be face to face or over the phone. Sessions will be scheduled at the Caregiver’s convenience.
- 2) The Program Coach will complete the Baseline interview including the Risk Assessment, which answers questions about the Veteran’s condition and Caregiver concerns. The Data Collector will complete the RPI/Assessment with the Caregiver at the End of Intervention (3 month) and 6 month interviews.
- 3) The Program Coach will complete an Intervention Delivery Assessment form, detailing location of session, date, and content for each session. For the last session, after Review, the Program Coach will provide support and encouragement to the Caregiver.
- 4) The Caregiver Notebook will contain materials and worksheets designed for possible session topics, available published educational materials for each topic, and resources for the red flags.

Red Flags - guide for unsafe or dangerous behaviors - include information on Abuse, Suicide Prevention, and Understanding & Dealing with Anger.
- 5) The Caregiver Notebook will structure the materials used by Caregivers during each session, serve as a “central location” to place all materials, and provide a resource after the session’s end.
- 6) **REACH VA MS topics** are structured according to the expressed needs of Caregivers of Veterans with MS. Each didactic component of the topic is based on the sanctioned materials with the addition of CBT content from our work with OEF/OIF troops and spouses, veterans with PTSD, and dementia caregivers:

Session and Topic	Content/Structure

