Assessment & Session 1 Stress Management	Caregiver Assessment/Baseline Interview Ask CG to tell story Introduce Intervention Review Caregiver Notebook and Mobility Chapters Discuss effects of stress Introduce stress management technique, Signal Breath Discuss physical therapy appointment Obtain closure to session
Session 2 Problem Solving	Introduce Session Review/modify last session commitment - Signal Breath Provide general information about MS and Exercise Brochures Present safety material (including alerts if appropriate) Introduce health care issues and Health Guide Problem Solve – Target Problem #1 Obtain closure to session
Session 3 Problem Solving and Mobility	Introduce session Review/modify Problem Solving Plan #1 Make Commitment for Problem Solving Plan #1 Introduce Mobility and Wellness Chapters Problem Solve Mobility Plan Obtain closure to session

Session 4 Mood Management and Mobility	Introduce session Review/modify Mobility Plan and Check in on PT appointments Make Commitment for Mobility Plan #1 Review/modify Problem Solving Plan #1 Make Commitment for Problem Solving Plan #1 Introduce stress management technique, Mood Management Obtain closure to session
Session 5 Problem Solving or Mood Management	Introduce session Review/modify stress management technique, Mood Management Problem Solve – Identify Target Problem #2 or Work on another Mood Management Thought Record Offer stress management technique, Stretching, Power of Music, Guided Imagery, or Pleasant Events Obtain closure to session
Session 6 & Closure Problem Solving, Stress Management, Mood Management, and Mobility review	Introduce session Review/Modify Mobility Plan and Problem Solving Plan #1 and #2 Offer stress management techniques, Stretching, Power of Music, Guided Imagery, or Pleasant Events Present REACH VA Review Worksheet Obtain closure to session

PROGRAM COACH FORMS FOR INTERVENTION

The Program Coach must complete different forms throughout the intervention. Below is a brief description of each form:

- ❑ **Risk Assessment**: This form is used to record areas of risk in safety, caregiving skills, social support, Caregiver emotional and physical well-being, and Veterans problems/concerns. This form will be completed as part of the Baseline, 3, and 6 month interviews.

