- Consent is reviewed during informed consent before completing the baseline assessment. The potential participants will be asked to read the informed consent and given the opportunity to ask questions. A Research Associate will review all of the key aspects of the study with the potential participants. Staff will question the potential participants to ascertain whether he/she has understood the information. Potential participants who are illiterate or have impaired vision will have the consent read to them and will be given an opportunity for questions and discussion. A signed informed consent is required prior to data collection. Participants will be encouraged to ask for clarification about the forms and discuss concerns about the study at this time.
- Consent will take place face to face for both the Caregiver and Veteran either in the Neurology department conference room or in the Research conference room.

- The consent form is carbon color coded. After the Caregiver/Veteran initials and signs the form, one copy of each page is kept by both, and one is filed in the study office.
- After consent is obtained, the baseline data collection will be completed for both the Veteran and Caregiver. The Caregiver will also complete the RPI/Assessment as part of the Baseline interview. The Caregiver will receive a REACH VA MS Caregiver Notebook and learn more about the REACH VA MS intervention from the REACH VA Program Coach. Caregivers can complete session 1 at this time or can schedule to complete session 1 over the phone within 7 days. No more than 7 days, with a goal of 1 to 5 days, can pass from baseline to intervention. If this happens, the Program Coach must complete a Protocol Variation form and check the box beside First REACH VA MS session more than 7 days from baseline interview.
- The follow-up data collection will occur at the end of the intervention (3 months) and 6 months. If either interview is completed 14 days prior or 14 days after the due date, the data collector must complete a Protocol Variation form and check the box under Data Collection that says Follow-Up completed outside of the window. Then, choose which interview was completed outside the window (3 or 6 month).
- The data collector has 2 weeks to complete data entry from day data was collected.

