Paper forms of the research records are kept in secure locked files in the project office. Electronic data is stored on a VA server folder that only local VAMC project research staff can access. After the study is completed, paper data will be stored with other completed research studies in a secured storage area. Records will be maintained and/or destroyed in accordance with the VA Records Control Schedule (RCS 10-1). For electronic information, as stated in the consent form, research information is analyzed for many years after a study, therefore, no specific date can be provided when this information will be destroyed or no longer used.

SCHEDULE OF DATA COLLECTION ASSESSMENTS

Time Frame for Caregiver		
Baseline (Face to Face) After consent signed and before intervention	Second (Telephone or Face to Face) 3 months (+/-14 days)	Third (Telephone or Face to Face) 6 months (+/-14 days)
X	X	X

Time Frame for Veteran		
Baseline (Face to Face) After consent signed	Second (Face to Face) 3 months (+/-14 days)	Third (Face to Face) 6 months (+/-14 days)
X	X	X

MEASURES

Data collection will occur at baseline, End of Intervention (3 months), and 6 months either face to face or by telephone. Data collection will take 30 minutes to an hour, based on face-to-face and telephone data collection in our work with OEF/OIF spouses and soldiers, and stressed caregivers, using the same and similar instruments (Table 3). We have used telephone and face to face batteries of similar length for older caregivers, who have not reported difficulty with these methods of data collection. If interviews completed over the phone, we will send response cards to the participant to make answering more efficient. The same RA will perform all data collection for a participant.

Measures were specifically chosen 1) to capture the mechanisms of action related to the theoretical model for individual stress process, and 2) to map onto measures being used by Multiple Sclerosis clinicians and researchers to provide maximum utility and generalizability for the study results.

If the Veteran/Caregiver team withdraws from the study, we will try to complete an abbreviated program evaluation to determine the reason for withdrawal.

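### The documents disagree on who administers the caregiver Risk Priority Inventory; on one reading the assessor changes between baseline and follow-up in a single-arm study

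*Combined protocol and SAP*

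**What the plan says.** All places are in the combined protocol and SAP.

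- **Session Structure, item 2**, on baseline: "The Program Coach will complete the Baseline interview including the Risk Assessment". On follow-up: "The Data Collector will complete the RPI/Assessment with the Caregiver at the End of Intervention (3 month) and 6 month interviews".
- **Research Methods, Data Collection**: "A trained masters-level Research Associate will collect data from Caregiver and Veteran by telephone or at clinic visits", with baseline, 3 months and 6 months named as the time points.
- **Measures**: "The same RA will perform all data collection for a participant". This is the only place that requires the same person throughout. Research Methods says only that a Research Associate collects the data.
- **Intervention – Overview**, in the Coach's session tasks: "Assess Caregiver risk in Session 1 using Risk Assessment". The session table's first row, which covers assessment and Session 1, begins "Caregiver Assessment/Baseline Interview Ask CG to tell story".
- **Program Coach Forms for Intervention**: the Risk Assessment is the first form listed as the Coach's to complete, and it is placed in the baseline, 3-month and 6-month interviews.
- **Screening and Consent**: "The Caregiver will also complete the RPI/Assessment as part of the Baseline interview". No administrator is named.
- **Incentives for Retention, item 2**: the same Research Associate is promised at each follow-up call; baseline is not mentioned.

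The Measures and Time table lists the 57-item RPI as a caregiver measure at study entry and follow-up. The Outcomes section places it under Caregiver Outcomes, covering among other things patient safety issues and the number of, and distress about, patient concerns. The design is pre-post, and Data Analysis compares baseline with 3 and 6 months.

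**The concern.** The Coach and the person collecting data are different people. Research Methods says "consent can be obtained by the Research Associate or Program Coach", and Screening and Consent has the Coach notify the data collector when sessions are stopped. Item 2 therefore assigns the baseline RPI to someone other than the Research Associate, contrary to Research Methods and Measures.

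If item 2 is what staff follow, the assessor changes exactly at the contrast the study relies on. The baseline RPI would be taken by the person about to deliver the intervention, and both follow-up RPIs by someone else. A caregiver may disclose more, or less, to a coach who is building rapport than to a data collector. With no control arm, that difference is part of the observed baseline-to-follow-up change. If every baseline were taken by the Coach, no analysis could remove it. It could create an apparent improvement or hide a real one.

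**Working it through.** **Step 1. The passages side by side**

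| Place | Baseline RPI | 3- and 6-month RPI |
|---|---|---|
| Session Structure, item 2 | Program Coach | Data Collector |
| Research Methods, Data Collection | Research Associate | Research Associate |
| Measures | same RA | same RA |
| Program Coach form list | Coach (possible reading) | Coach (possible reading) |
| Intervention – Overview; session table | in the Coach's Session 1 | not addressed |
| Screening and Consent | not named | not named |
| Incentives for Retention, item 2 | not addressed | same Research Associate |

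Taking the Data Collector to be the Research Associate, item 2 agrees with Research Methods at follow-up and conflicts with it at baseline.

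Four further places lean toward the Research Associate at baseline. Screening and Consent puts baseline data collection ahead of Session 1, which may follow by up to 7 days. The risk section has a Coach available to help a distressed participant during data collection, baseline included, which implies that someone else is asking the questions. Data Management has interviewers certified on the assessment and follow-up interviews. Measures has the Research Associate read the interviewer manual.

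**Step 2. Consequence under each reading**

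- Same Research Associate throughout: no change of assessor.
- Coach throughout: no change of assessor, but the treating person collects an outcome.
- Item 2: the assessor changes between baseline and 3 months, and again for baseline against 6 months. The 3-to-6-month contrast has the same assessor role at both ends.

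**Step 3. Scale, as an illustration only**

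The plan gives no assessor effect, RPI standard deviation or RPI correlation, so there is no plan figure to reproduce.

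Inputs:
- Caregivers completing: 25 pairs less 15% attrition, 25 × 0.85 = 21.25, so 21. If the 50 subjects in Data Analysis means 50 caregivers, 50 × 0.85 = 42.5, so 42.
- Assumed assessor shift s: 0.1, 0.2 and 0.3 SD. The middle value equals the plan's threshold for clinical significance. None is a document estimate of an assessor effect.
- Assumed correlation ρ: 0.3 to 0.7. Table 1 (N = 125, dementia programme, shorter scales) gives a rough guide if its p values come from paired t tests. SD of change = (mean change / t) × √125, and ρ = (SD₁² + SD₂² − SD of change²) / (2 × SD₁ × SD₂).
  - Behaviors (p = .001): t = 3.37; SD of change = 1.2/3.37 × 11.18 = 3.98; ρ = (3.7² + 4.6² − 3.98²)/(2 × 3.7 × 4.6) = 0.56.
  - Depression (p = .006): ρ about 0.39.
  - Behaviors bother (p = .164): ρ about 0.35.

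Method: paired t test, two-sided 0.05, true change zero. The standardised shift is dz = s/√(2(1 − ρ)), and the rejection probability comes from the noncentral t distribution with noncentrality dz × √n. For s = 0.2, ρ = 0.3 and n = 21: dz = 0.2/√1.4 = 0.169, noncentrality 0.775, rejection 11.4%.

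| n | Shift (SD) | ρ = 0.3 | ρ = 0.56 | ρ = 0.7 |
|---|---|---|---|---|
| 21 | 0.1 | 6.6% | 7.5% | 8.7% |
| 21 | 0.2 | 11.4% | 15.4% | 20.3% |
| 21 | 0.3 | 19.8% | 28.7% | 39.4% |
| 42 | 0.2 | 18.8% | 27.1% | 37.2% |

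With no shift, as in the 3-to-6-month contrast, the rate is 5%. A three-time-point repeated measures ANOVA under compound symmetry, with n = 21 and s = 0.2, gives 11.0%, 14.9% and 20.0%. The ρ = 0.7 column lies above all three correlations derived from Table 1, so it is an upper case.

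**The case against.** The strongest reply is that item 2 is a drafting slip. Most of the data collection text points to the Research Associate, and the Coach's Risk Assessment in Session 1 can be seen as an intervention tool rather than outcome collection. The plan also has safeguards: interviewers are certified, questions are asked as written, audiotaped interviews are scored with 90 as the acceptable mark, and there are question-by-question instructions. These would limit drift between assessors. Much of this stands. It does not settle the matter, because item 2 is explicit, the session table and Intervention – Overview fit it, and the documents do not say that the Coach is certified as an interviewer.

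A reader might infer more than the documents support:

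- **That PHQ-9, GAD-7 and Zarit change hands too.** Item 2 gives the baseline interview to the Coach but names the follow-up assessor only for the RPI. For these scales, the only ones in the power table, the change is an inference.
- **That item 2 is the only text naming an administrator, so a change of assessor is certain.** The Program Coach form list can be read as giving the form to the Coach at all three visits, with no change.
- **That the results are biased toward benefit.** Nothing in the documents gives the direction or size of an assessor effect.
- **That the rejection rates describe this trial.** The shift is assumed, and the correlations come from different scales in another population.

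The flow charts, the Manual of Operations volumes and a short part of the protocol could not be read for this review. Any of them might assign the role.

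**Conclusion.** The contradiction is real and stands in the current text: item 2 cannot be followed together with Research Methods and Measures, and the Coach form list adds a possible third version. The consequence is conditional. Only if item 2 is followed is an assessor difference inseparable from the baseline-to-follow-up change in the RPI outcomes. The true size is unknown. The illustrative 11 to 20% for a 0.2 SD shift depends on that assumed shift, 21 completing caregivers and a correlation of 0.3 to 0.7.

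Severity is minor: this is a feasibility study, no powered outcome is shown to be affected, and the interview safeguards may limit the effect. Which instrument supplies the problem and safety-alert counts in Hypothesis 2 is a separate question and is not part of this point.

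**What to change.** Reconcile these places to Research Methods and Measures: Session Structure item 2, the Risk Assessment task in Intervention – Overview, the first row of the session table, the Risk Assessment entry in the Program Coach form list, and Incentives for Retention item 2 (extend it to baseline). They should all say the following:

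- The same Research Associate administers the caregiver outcome battery, including the RPI used as outcome data, at baseline, 3 and 6 months.
- The Research Associate passes the completed baseline form to the Coach for use in Session 1. Any entries the Coach makes are intervention records, not outcome data.
- The assessor is recorded at each visit.
- If any baseline RPI was taken by the Coach, the number is reported and the RPI baseline-to-follow-up change is labelled as assessor-confounded.

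The cost is wording edits in five places and one extra field per visit, with no new visit or staff. The practical downside is timing: the completed 57-item form must reach the Coach before Session 1, which may be the same day.
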